Disease Evaluations											
PSA ^{j,b}	j, k	X ^k	X ⁱ			X	X		X	X	X ⁱ
Testosterone		X					X		X	X	
CT and bone scans ^{k,l}	k,l	X ^{k,l}									
Correlative Evaluations											
CPET	9.12.3		X			X			X		
Chair Stand	9.12.3		X						X		
Timed Up and Go	9.12.3		X						X		
6 min walk distance (Duke patients only)	9.12.3		X						X		
Musc. Strength ⁿ	9.12.3		X		X ^q			X ^q	X		
Muscle CSA ^s (protocol v1-v15 only)	9.12.3		X						X		
Musc. Endur. ⁿ	9.12.3		X		X ^q			X ^q	X		
FACT-P	9.12.3		X						X	X	
FACIT-Fatigue	9.12.3		X						X	X	
Godin Leisure Time Exercise	9.12.3		X						X	X	
Food Frequency Questionnaire	9.12.3		X						X		

Fasting glucose, insulin, HgbA1C ^s (protocol v1-v15 only)	9.12.3		X					X		
Body Composition ^r	9.12.3		X					X		
Metabolomics	9.12.3		X				X	X		
Treatment										
Exercise Training (ARM B ONLY) ^p	9.5-9.6			X	X	X	X	X		
Enzalutamide	9.6					X	X	X	X	
ADT ^m	9.6					X	X	X		

NOTE: The Safety Follow-Up visit will occur in conjunction with the End of Treatment visit 30 days after the last dose of enzalutamide or prior to initiation of cytotoxic or investigational therapy, whichever occurs first.

- a. Unscheduled visits may be performed at any time during the study as clinically indicated to assess for or follow-up on adverse events. Unscheduled visits may also occur due to holidays or other scheduling difficulties and in between week 17 and week 37 as clinically indicated.
- b. Informed consent may be performed within 42 days prior to enrollment (Day 1), but must be obtained prior to the performance of any study-specific procedures.
- c. Randomization should be performed within 30 days after baseline testing (specifically, CPET) is completed, but only after eligibility is confirmed and up to 14 days prior to Day 1. **See also footnote p. below.**
- d. A complete physical examination is required at the Screening, Day 113, and Day 252 visits. A brief symptom-directed physical examination should be performed at all other clinic visits.
- e. Vital signs (temperature, blood pressure, heart rate) are to be obtained at each visit.
- f. Performance status by Eastern Cooperative Oncology Group (ECOG) scoring (**Appendix A**).

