- g. Exercise-related adverse events will be collected from baseline/screening through the End of Study visit for all subjects. All other adverse events will be collected from the start of study drug. Serious adverse events are recorded from the time the informed consent form is signed until the Safety Follow-Up visit (or screen failure). In the event of no Safety Follow-Up visit, adverse event information will be collected through 30 days after the last dose of study drug. Subjects should be contacted by phone for adverse event follow-up if they do not come to the clinic for the Safety Follow-Up visit.
- h. Clinical laboratory tests may be performed at unscheduled visits if clinically indicated.
- i. Labs performed as part of screening are good for 30 days before randomization and do not need to be repeated.
- j. PSA may be performed at Unscheduled Visits as indicated to confirm PSA progression. No subject should discontinue study drug due to PSA rise during the first 12 weeks of therapy. Subjects with PSA progression on or after Week 17 must have progression confirmed by a second consecutive assessment conducted at least 3 weeks later before study drug discontinuation.
- k. CT of the abdomen and pelvis and bone scans should be performed to document that there is no definite evidence of metastatic disease at the time of screening. MRI of the abdomen and pelvis may be used in place of the CT.
- l. Baseline imaging performed per NCCN Guidelines⁸⁶ prior to informed consent as standard of care may be used so long as it is performed within 84 days prior to randomization.
- m. ADT (GnRH analogue) will be administered as per standard of care to maintain a castrate level of serum testosterone (<50 ng/dL) from Day 29 to Day 252.
- n. Muscular Strength and Muscular Endurance must be done at least 24 hours before or after CPET to allow adequate recovery time.
- o. Both the usual care group and the exercise training group will have a 4 week lead-in before starting ADT plus enzalutamide; only the exercise training group will undergo exercise training during this time.
- p. Day 1 is defined as the randomization day for Arm A (non-exercise) and the start of exercise for Arm B.
- q. Randomization may be done on Day 1 prior to the patient's exercise training session(s) for that week.
- r. DEXA scan for body composition should be fasting, if possible.

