9.5 Lead-In Period

Subjects will be randomized to usual care or exercise training up to 14 days prior to Day 1, but only after eligibility is confirmed and baseline exercise testing (specifically, CPET) has been performed. See **Sections 6.1.4** and **9.4** for randomization details. See also **Schedule of Events**, above.

Arm A, ENZ – ADT plus Usual Care: Subjects randomized to usual care will be asked not to make any changes in their physical activity beginning on Day 1. These subjects will start ENZ – ADT on Day 29 (week 5) after the 4 week lead-in period. This delay is felt to be insignificant from a clinical perspective. While two Phase III studies are currently examining this question (NCT00439751; NCT00110162), the delay in initiation of ADT in these studies is much longer than 4 weeks. There is currently no evidence that a delay, especially one as short as 4 weeks, in starting ADT in men with non-metastatic prostate cancer, affects outcomes.⁸⁸

Arm B, ENZ – ADT plus Exercise Training: Subjects randomized to exercise training will begin the exercise training program detailed below beginning on Day 1. The goal for the ENZ-ADT plus exercise training will be 3 supervised exercise sessions per week at an intensity between 50 and 100% of the individually determined exercise capacity (at baseline) for aerobic training and an intensity between 60% and 80% of one-repetition maximum (1-RM) for resistance training for 30-90 minutes/session. The exercise training intervention is designed such that participants begin exercising at a low intensity (~50%-60% VO₂peak) that is subsequently increased to more moderate to vigorous intensity (~70%-80% VO₂peak) when appropriate. All interventions will be individually tailored to each subject following the principles of aerobic or resistance training prescription guidelines for adults as recommended by the American College of Sports Medicine (ACSM).⁸⁹ All exercise sessions will also be performed in a supervised setting with one-on-one supervision by certified exercise physiologists, physical therapists, exercise physiology students under the supervision of an ACSM-certified exercise physiologist, or trained designee. The exercise prescription for each subject will be created centrally by either [name] group at MSKCC or the CPX Lab at Duke based on both the interpretation of the CPET plus Muscular Strength/1-RM data and a standardized template, within 24-48 hours of these tests.

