10.1 Adverse Events

An adverse event (AE) is any untoward medical occurrence in a subject undergoing a study procedure/intervention and/or receiving study drug; which may or may not have a causal relationship with study procedures, interventions or treatments. For this protocol, the definition of AE also includes worsening of any pre-existing medical condition. An AE can therefore be any unfavorable, unintended or worsening sign or symptom (including an abnormal laboratory finding, or disease temporally associated with exercise testing for both arm A and arm B; exercise training for arm B; and/ or related to the use of enzalutamide. Abnormal laboratory findings without clinical significance (based on the PI's judgment) should not be recorded as AEs. But laboratory value changes that require therapy or adjustment in prior therapy are considered adverse events.

Research exercise-related adverse events will be collected from the baseline exercise testing to the End of Study visit (as defined in **Section 9.8**) for all subjects (Except anticipated AEs-see section 10.1.2). All subjects will have enzalutamide related adverse events collected from the start of study drug on week 5, day 29 through the Safety Follow-up visit.

Serious adverse events that are related to study exercise procedures (CPET, 1RM, Chair testing, etc) are recorded from the time the informed consent form is signed until the Safety Follow-Up visit (withdrawal or screen failure). All SAEs will be collected regardless of attribution starting once the patient takes his first dose of study drug through the Safety Follow-Up visit. All AEs and SAEs must be recorded in the subject medical record and adverse events case report form.

AEs will be assessed according to the CTCAE version 4.0. If CTCAE grading does not exist for an AE, the severity of the AE will be graded as mild (1), moderate (2), severe (3), life-threatening (4), or fatal (5).

Attribution of AEs will be indicated as follows:

- Definite: The AE is clearly related to the study drug and/or exercise training and/or exercise testing
- Probably: The AE is likely related to the study drug and/or exercise training and/or exercise testing
- Possible: The AE may be related to the study drug and/or exercise training and/or exercise testing
- Unlikely: The AE is doubtfully related to the study drug and/or exercise training and/or exercise testing

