10.2.1 Reporting of SAEs

Serious adverse events, whether or not considered drug related, should be reported to the lead site/sponsor (Duke) within 24 hours of becoming aware of the event, using the provided DCI SAE Report Form and the SAE Report Review Form (Site Assessment). These documents should be sent to:

The DCI Safety Desk – fax: [REDACTED]

If the safety desk cannot be reached within 24 hours, the Principal Investigator should be contacted: [name], [REDACTED]; email: [contact]

The initial report for each SAE or death should include at minimum the following information:

- Protocol # and title
- Patient initials, study identification number, sex, age
- Date the event occurred
- Description of the SAE
- Dose level and cycle number at the time the SAE occurred
- Description of the patient's condition
- Indication whether the patient remains on study
- Causality

Follow-up information including severity, action taken, concomitant medications, and outcome should be communicated to Duke as soon as possible.

Upon receipt of the Serious Adverse Event Reporting form by the DCI Safety Desk, the PI will be notified and be required to complete the PI assessment of the DCI Safety SAE Report Review Form. The DCI safety desk will, in turn, report the event to Astellas if felt to be at least possibly related to enzalutamide using the DCI SAE Report Form.

The SAE documentation, including the DCI SAE Report Form and available source records should be emailed or faxed to:

Astellas Pharma Global Development – United States
 Email: [REDACTED]
 Fax number: [REDACTED]

The following minimum information is required:

- Study number/IIT regulatory identifier
- Subject number, sex and age
- The date of report
- A description of the SAE (event, seriousness of the event)
- Causal relationship to the study drug

Follow-up information for the event should be sent within promptly (within 7 days) as necessary.

Follow-up information for the event should be sent within promptly (within 7 days) as necessary.

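### The SAE rules conflict before the first dose: a lead-in SAE judged unrelated to exercise is recorded under Schedule footnote g but not under Section 10.1

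*Combined protocol and SAP*

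**What the plan says.** The Schedule of Events in Section 9 gives a single rule for SAEs in footnote g: "Serious adverse events are recorded from the time the informed consent form is signed until the Safety Follow-Up visit (or screen failure"). The sentences just before it split ordinary adverse events by cause: exercise-related ones count from screening, all others from the start of study drug. The SAE sentence has no such split.

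Section 10.1 gives a two-stage rule. The first stage is limited by cause: "Serious adverse events that are related to study exercise procedures (CPET, 1RM, Chair testing, etc) are recorded from the time" of consent. The second stage has no such limit but starts later: "All SAEs will be collected regardless of attribution starting once the patient takes his first dose of study drug through the Safety Follow-Up visit".

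Section 10.2.1 covers reporting: "Serious adverse events, whether or not considered drug related, should be reported to the lead site/sponsor (Duke) within 24 hours" of awareness. It gives no start date.

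Study drug begins "on Day 29 (week 5) after the 4 week lead-in period" (Section 9.5, stated for Arm A; Section 9.6 gives the same day for Arm B). During those four weeks, "only the exercise training group will undergo exercise training during this time" (Schedule, footnote o).

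**The concern.** Two current passages give different answers to a basic question: does an SAE that occurs before the first dose, and is thought to have nothing to do with exercise, go into the trial database?

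The period affected includes the lead-in, the only time when Arm B trains without drug and Arm A has neither. Section 5 lists the safety of exercise training as a secondary objective and the adverse event rate in each arm as part of its endpoint. The trial is open label (Section 6.1.4). If Section 10.1 is followed, staff who know the arm decide whether a lead-in SAE is related to exercise, and that decision determines whether it is recorded at all. The natural direction is uneven: a link to exercise is more readily considered in a man who is training than in one who is not, so an unrelated-looking event is more easily left out in Arm A.

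Two sites run the trial, and each could follow a different passage in good faith. Routine monitoring is light (Section 11.1: 1 to 3 subjects a year after the first visit), so a divergence could go unnoticed.

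**Working it through.** The plan gives no figure on this point to reproduce. The check is a comparison of the rules and a count of days.

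**1. The rules applied to an SAE on Days 1–28**

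| SAE in the lead-in | Footnote g | Section 10.1 |
|---|---|---|
| Related to an exercise test (CPET, 1-RM, chair test) | Recorded | Recorded |
| Related to exercise training (Arm B) | Recorded | Probably recorded; the parenthesis names only tests, then etc |
| Judged unrelated to exercise | Recorded | Not recorded |

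The third row is the contradiction. The two rules cannot be merged by reading footnote g as a summary of Section 10.1: if all SAEs already counted from consent, the second-stage sentence in Section 10.1 would have no purpose.

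**2. Does another passage settle it?**
- Section 10.2.1 disregards drug attribution but has no start date.
- Section 10.1 closes by requiring AEs and SAEs to be entered in the medical record and CRF, again with no start date.
- Section 13.5 sends the reader to Sections 11.6 and 11.7 for monitoring detail; Section 11 ends at 11.2.4.

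None of these decides which window applies.

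**3. Length of the window**
- Lead-in: Day 1 to Day 28 = 28 days. With the ±3-day window on Day 29 it is 25 to 31 days.
- Both rules start at consent, and "Informed consent may be performed within 42 days prior to enrollment (Day 1"), so they differ for at most 42 + 28 = 70 days per man. The first 42 of these precede any training.

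**4. Time at risk in the lead-in** (20 men per arm, Section 12.6)
- Per arm: 20 × 28 / 365.25 = 1.53 person-years. Range with the Day 29 window: 20 × 25 / 365.25 = 1.37 to 20 × 31 / 365.25 = 1.70.
- Both arms: 40 × 28 / 365.25 = 3.07 person-years.

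**5. Weight of one event**
- 1 / 20 = 5 percentage points of an arm's proportion with an SAE.

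**The case against.** The strongest defence is that Section 10.1 is the intended rule. The adverse event row of the Schedule points to Section 10, and a two-stage rule, exercise-related before drug and everything after, is coherent. Safeguards also exist: 24-hour reporting to a single safety desk, an instruction to assess AEs and SAEs at every visit (Section 10), and an adverse event check on Day 29. Adverse event rates are only displayed by arm, with no test planned (Section 12.5), and the primary endpoint is untouched.

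Much of this stands and limits the point. It does not remove it. Nothing gives Section 10.1 precedence over footnote g. The safeguards have no start date, so they lower the risk without deciding the question. A descriptive comparison still needs both arms ascertained in the same way.

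Two stronger readings are tempting and should be set aside.

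- A reader might infer that SAEs caused by training itself escape Section 10.1, because its parenthesis lists only tests. The documents point the other way. The list is open-ended, the adverse event definition in the same section includes Arm B training, every level of the attribution scale names training, and exercise-related events are collected from baseline testing. Section 10.1.2 also lists cardiac and cerebrovascular events as possible effects under a heading that covers training and testing, so a cardiac event in a man in training is unlikely to be dismissed. Some looseness remains, because the recording sentence in Section 10.1.2 names CPET only.
- A reader might count all time from the earliest consent: 40 × 70 / 365.25 = 7.67 person-years. Of that, 40 × 42 / 365.25 = 4.60 falls before Day 1, before any training and largely before randomisation, and it assumes that every man consents on the earliest possible day. It says little about exercise safety or the arm comparison.

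**Conclusion.** The point holds in a narrow form. Footnote g and Section 10.1 contradict each other on SAEs before Day 29 that are judged unrelated to exercise. If Section 10.1 is followed, such events in the lead-in are lost, and which events are lost depends on an unblinded judgement that can differ by arm.

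The time at risk is about 1.5 person-years per arm (3.1 in both). The documents give no event rate, so the number of lost events cannot be estimated; that it is small is my assumption, based on the short exposure. With 20 men per arm, even one missed SAE shifts the per-arm proportion visibly.

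The loss occurs only where Section 10.1 is the rule in use. A reader might infer that the sites already work to different rules or that events have been hidden; nothing in the documents shows either. The sponsor should correct this, but it does not threaten the primary analysis.

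**What to change.** State one SAE window in identical words in footnote g, Section 10.1 and Section 10.2.1:

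- Collect and report all SAEs regardless of attribution, in both arms, from consent or at the latest from randomisation, to the Safety Follow-Up visit or screen failure.
- Record attribution to drug, training and testing in a separate field, so that it describes an event and does not decide whether it is captured.
- Name exercise training explicitly wherever exercise procedures are listed.

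The documents require only that the passages be reconciled. Preferring the attribution-free window is a judgement, made because it is the only one of the two that treats both arms alike in the lead-in. If randomisation is chosen as the start, Section 9.4 lets Arm B be randomised up to 14 days before Day 1, so the by-arm summary should show time at risk. Section 6.1.4 limits CRFs to registered and randomised men, which should be squared with an SAE window that reaches screen failures.

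The cost is protocol wording and a few extra SAE forms. The change cannot be fully prospective: at least 8 men had completed week 17 testing by November 2016 (Section 12.6), and the current text postdates protocol version 16 (25 May 2017). Men already past the lead-in can be covered only by retrospective record review, and the report should say which men were collected under which rule.

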5 OBJECTIVES AND ENDPOINTS

All endpoints will be evaluated at the time points specified in the Schedule of Events at the beginning of **Section 9**. See **Section 12** for Statistical Methods and Data Analysis. Key comparisons will be the change from Day 1 (week 1) to Day 113 (week 17), which corresponds to the end of the 16 week exercise training program for Arm B, and from Day 1 (week 1) to Day 252 (week 37), which corresponds to the end of the 32 weeks of treatment with enzalutamide and ADT for both Arms.

	Objective	Endpoint	Analysis
Primary	Compare cardiopulmonary function in usual care vs. exercise training arms	Change in $\text{VO}_{2\text{peak}}$ with usual care or exercise training at 16 weeks from baseline	See Section 12.1 to 12.4
Key Secondary	Compare the effects on physical functioning / functional capacity	Objective assessments (i.e., chair-stand test, timed up and go, 6 minute walk distance) of functional capacity	See Section 12.5
Other Secondary	Compare the effects on primary physiological determinants of $\text{VO}_{2\text{peak}}$	Upper and lower extremity maximal muscular strength (voluntary one-repetition maximum [1-RM]) and muscular endurance (repetitions to fatigue at 70% of 1-RM and muscle cross sectional area of the dominant thigh (3.0 T magnetic resonance imaging)	See Section 12.5
Other Secondary	Compare the effects on metabolic outcomes of interest	Metabolic control (fasting glucose, insulin, glycosylated hemoglobin, HOMA-IR) and body composition (lean and fat body mass)	See Section 12.5
Other Secondary	Compare the effects on patient reported outcomes (PROs) of interest	Quality of Life (FACT-P), Fatigue (FACIT-F), and Leisure Time Exercise Habits (Godin Leisure Time Exercise Questionnaire)	See Section 12.5
Other Secondary	Evaluate safety, feasibility, and acceptability of exercise training	Eligibility rate, acceptance rate, adherence rate, attrition rate, and adverse event rate (CTCAE v4.0) in each arm	See Section 12.5
Exploratory	Compare PSA response rates	Maximum decrease in PSA from baseline (waterfall plot)	See Section 12.5
Exploratory	Describe metabolomics changes	Targeted and untargeted metabolic profiling	See Section 12.5
Sensitivity	Assay the robustness of results observed in analyses based on the modified ITT population	Primary and Key secondary endpoints, using Last Observation Carried Forward methods	See Section 12.5

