- s. Muscle CSA and Fasting glucose, insulin, and HgbA1C will no longer be collected starting from Protocol v16 approval (5/25/17 moving forward). This applies to subjects currently enrolled and future enrollments.

UC, usual care; ADT, androgen deprivation therapy; BMI, body mass index; ECOG, Eastern Cooperative Oncology Group; CBC, complete blood count; PSA, prostate-specific antigen; CT, computed tomography; CPET, cardiopulmonary exercise test;1-RM, 1-repetition maximum (voluntary); CSA, cross-sectional area; Musc. Endur., muscular endurance; FACIT, Functional Assessment of Chronic Illness Therapy; FACT-P, Functional Assessment of Cancer Therapy-Prostate; HgbA1c, glycosylated hemoglobin.

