Muscular Endurance of the upper and lower body will be assessed as the *number of repetitions to fatigue at 70% of the 1-RM*. The same exercises and methods will be used as in the 1-RM determination, detailed above. Subjects will continue until technique, tempo, volition or inability to complete two consecutive repetitions causes finality (per discretion of the exercise physiologist or trained designee).

Metabolic Control (protocol v1-v15 only)

Subjects will undergo sampling of fasting, pre-exercise, **plasma insulin** and **glucose** concentrations for calculation of **HOMA-IR**, as previously described.⁹⁷ **Glycosylated hemoglobin** (HgbA1c) will also be measured. These will be measured in a CLIA-certified clinical laboratory.

Body Composition

Body composition will be assessed by dual energy x-ray absorptiometry scan in the morning (after an overnight fast, if possible). Transverse scans from head to toe measured absorption of x-ray beams at two different energy levels allowing for a valid determination of lean body mass, fat mass and fat percentage.

Patient Reported Outcomes

Data on health related quality of life will be collected using the Functional Assessment of Cancer Therapy-Prostate (**FACT-P**) scale, which can be found in **Appendix C**.^{98,99} Data on subject-reported changes in fatigue will be collected using the Functional Assessment in Chronic Illness Therapy – Fatigue questionnaire (**FACIT-F**), which can be found in **Appendix B**. Data on leisure time exercise habits will be collected using the 4-item **Godin Leisure Time Exercise Questionnaire**, which can be found in **Appendix D**.¹⁰⁰

Food Frequency Questionnaire (FFQ)

A food frequency questionnaire (FFQ) developed by the Nutrition Assessment Shared Resource (NASR) of Fred Hutchinson Cancer Research Center (FHCRC) will be administered at the Week 1 and Week 17 time points to explore the collinearity of diet/exercise and to potentially correct for imbalances in the dietary intake between arms. Participants will be queried regarding their dietary intake over the last 1 month prior to completing the questionnaire.

Specifically, nutrient data will be collected using the Men's Nutritional Assessment (MNA). Nutrition Assessment uses the University of Minnesota Nutrition Data Systems for Research (NDSR) software for data entry and nutrient analysis via the FFQ. A sample booklet is provided at:

<http://sharedresources.fhcrc.org/sites/default/files/FFQ-MNA-Sample.pdf>

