Questionnaires will be batched (approximately 30-40 questionnaires/batch) and sent via UPS/FedEx to NASR for scanning. FFQs are optically scanned at FHCRC. Each batch of scanned FFQs yields files containing food consumption data, nutrient intake data, and an error report that specifies questionnaire completion errors (e.g. incomplete erasures, missed questions).

Following is the contact information for the NASR:

Location: [name]
Mailing Address: [name]
Phone: [REDACTED]
Fax: [REDACTED]
Email: [REDACTED]
Contact: [name], M.S.,R.D.,C.D., Director

Prostate-Specific Antigen (PSA)

Prostate-Specific Antigen (PSA) will be measured in a CLIA-certified clinical laboratory.

Metabolomics

Fasting EDTA plasma will be collected from each participant at each time point and stored at -80°C for metabolic profiling. Refer to lab manual for blood collection volumes. Metabolic intermediates will be measured using a targeted, mass spectrometry (MS)-based platform as described previously.¹⁰¹ Profiling will include ~96 serum metabolic intermediates, hormones of energy regulation, and serum cytokines known to be associated with insulin sensitivity, exercise/diet induced changes, or treatment with ADT (**Table 2**). Our collaborators at the Stedman Center at Duke have reported sample preparation methodology and coefficients of variation for each assay.^{102,103} Cytokines and inflammatory markers will be measured using a Luminex panel. Conventional metabolites will be measured in a CLIA-certified clinical laboratory.

Table 2. Targeted Metabolomics Analysis – Metabolic Factors to be Assessed

Conventional Metabolites	C-reactive protein (CRP), glucose, total cholesterol, HDL, LDH, triglycerides, total free fatty acids, ketones, 2-OH butyrate, 3-OH butyrate, succinate, steroids (multiple ³⁵)
Energy Hormones	Insulin, ghrelin, adiponectin, leptin, glucagon, C-peptide, IGF-1, IGFBP-1, -2, -3, resistin

Cytokines	TNF- α , IL-1 β , IL-2, IL-6, IL-8, IL-10, IL-12p40, IL-12p70, IFN- γ
Amino Acids^{102,104,105}	Glycine, alanine, serine, proline, valine, leucine/isoleucine, methionine, histidine, phenylalanine, tyrosine, Asx (asparagine, aspartate, aspartic acid), Glx (glutamate/glutamine/glutamic acid), ornithine, citrulline, arginine
Acylcarnitines (AC)/Other¹⁰⁶	~30 selected AC, including C3, C5; medium and long chains; cholate; dicarboxylic acids

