For analysis of metabolomics, PCA analysis will be used to reduce the large number of correlated factors into a smaller number of dimensions. Unless otherwise noted, all analyses will be done separately for the usual care and exercise groups. Of primary interest is the association of metabolomic biomarkers with changes in both VO₂peak and HOMA-IR. Changes in metabolite concentrations and VO₂peak or HOMA-IR will be compared between the usual care and exercise groups using ANOVA. Correlation analysis and linear regression will be used to describe the relationship between metabolomics biomarker changes and VO₂peak or and HOMA-IR. Nominal statistical significance will be defined as p<0.05.

In addition, the maximum PSA change from baseline in each patient will be described using waterfall plots. The PSA response rate, defined as the proportion of men with a ≥80% decline in PSA from baseline, will be reported for each arm. The median decrease in PSA will also be reported for each arm.

Sensitivity analyses will be performed repeating primary endpoint and key secondary endpoint analyses using Last Value Carried Forward (LOCF) methods. The intent of this sensitivity analysis is to assay the robustness of results observed in the modified ITT population.

Adjustment for multiple comparisons is not planned for secondary or exploratory measures.

Rates of adverse events, classified by CTCAE v4.0, will be displayed by body system and preferred term for each arm.

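### Sections 5 and 12.5 still plan comparisons of HOMA-IR, HgbA1c and muscle CSA after their collection stopped at v16; HOMA-IR could be derived for all men from the metabolomics plasma, but the plan does not say so

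*Combined protocol and SAP*

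**What the plan says.** **What stopped.** Footnote s to the Schedule of Events (Section 9) says: "Muscle CSA and Fasting glucose, insulin, and HgbA1C will no longer be collected starting from Protocol v16 approval (5/25/17 moving forward"), and adds: "This applies to subjects currently enrolled and future enrollments". The schedule and Sections 9.3, 9.6 and 9.12.3 are annotated to match. In 9.12.3 the definition of HOMA-IR sits under the heading "Metabolic Control (protocol v1-v15 only").

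**What did not change.** Section 5 still lists, under objectives to compare the arms, "muscle cross sectional area of the dominant thigh (3.0 T magnetic resonance imaging") and "Metabolic control (fasting glucose, insulin, glycosylated hemoglobin, HOMA-IR"). Section 12.5 says, of the metabolomics analysis: "Of primary interest is the association of metabolomic biomarkers with changes in both" VO2peak and HOMA-IR. It plans a between-arm ANOVA for HOMA-IR, plus correlation and regression, by default separately in each arm, with nominal significance at p<0.05. No analysis set, minimum number or missing-data rule is given for the truncated measures.

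**What continues.** Fasting, pre-exercise metabolomics plasma is drawn at baseline (9.3) and at Days 57 and 113 (9.6), with no v1-v15 restriction. Section 9.12.3 has it taken from every participant and stored at -80°C. Table 2 lists glucose among the conventional metabolites, and its energy hormones begin "Insulin, ghrelin, adiponectin, leptin, glucagon, C-peptide". Nothing says that HOMA-IR will be calculated from these values.

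**The concern.** The operational sections were amended and the endpoint and analysis sections were not. An analyst following the text would compute HOMA-IR from the clinical fasting glucose and insulin, and so only in early enrollees. The ANOVA and the within-arm correlations would then run on a small subset defined by calendar date, with a p<0.05 label attached. A non-significant result from a few men per arm could be read as no effect of exercise on insulin resistance. Meanwhile both inputs to HOMA-IR are on a panel planned for every man.

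**Working it through.** **1. The plan's own figure.** Section 12.6 gives 20 per arm for 80% power at 0.68 SD, significance level 0.10, one-sided. By the normal formula, n = 2(1.2816 + 0.8416)²/0.68² = 2 × 4.508/0.4624 = 19.5, so 20. The exact noncentral t gives 80.1% power. The figure reproduces, but it concerns VO2peak; no power target is stated for CSA, HgbA1c or HOMA-IR.

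**2. Who can have paired values.** The stop covers men already enrolled, so a paired value needs a Day 113 visit before 25 May 2017. Day 113 is 112 days after Day 1, which puts Day 1 at about 2 February 2017 or earlier. With the 7-day window (105 days) the limit is 9 February 2017. Men between baseline and Day 113 on that date have a baseline value only. CSA loses further men, because 9.12.3 omits the MRI when the screening form is positive.

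**3. How many.** The documents do not say. The nearest count is in 12.6: 8 men (4 per arm) with week-17 VO2peak in November 2016, with accrual described as slow. I assume 4 to 10 pairs per arm.

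**4. Precision over that range.** I use two-sided 0.05, since Section 12.5 sets nominal p<0.05 for the HOMA-IR analyses.
- Detectable difference d: solve P(T > t(0.975, 2n-2)) = 0.80, with T noncentral t and noncentrality d√(n/2).
- 95% CI half-width for the difference, in SD: t(0.975, 2n-2) × √(2/n). For n=4, 2.447 × 0.707 = 1.73.
- Smallest significant within-arm correlation: |r| = t/√(n-2+t²), with t = t(0.975, n-2). For n=10, 2.306/√(8+5.318) = 0.63.

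| n per arm | Detectable d (SD) | CI half-width (SD) | Critical \|r\| |
|---|---|---|---|
| 4 | 2.38 | 1.73 | 0.95 |
| 8 | 1.51 | 1.07 | 0.71 |
| 10 | 1.32 | 0.94 | 0.63 |
| 20 | 0.91 | 0.64 | 0.44 |

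At the primary endpoint's one-sided 0.10, the detectable d would be 1.62 (n=4), 0.97 (n=10) and 0.68 (n=20).

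**5. What recovery buys.** Using the metabolomics plasma returns HOMA-IR to at most 20 per arm. Section 6.3 cites a HOMA-IR change of +45.1% (SD 192.5%) at 25 weeks on enzalutamide monotherapy. If that SD applied here, a between-arm difference of 45.1 points would be 45.1/192.5 = 0.234 SD. Power at 20 per arm would be about 11%, and 80% power would need 2(1.960 + 0.842)²/0.234² ≈ 286 per arm. The 0.91 SD detectable at 20 per arm corresponds to about 175 percentage points.

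**The case against.** The strongest reply is that the amendment is already visible. Section 5 ties all endpoints to the Schedule of Events, which carries footnote s. Section 12.5 calls comparisons of secondary endpoints descriptive, and the trial calls itself a pilot. Computing HOMA-IR from Table 2 is also a permissible reading, since the HOMA-IR analyses stand in the metabolomics paragraph.

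Part of this stands. The restriction is not hidden, and labelling CSA and HgbA1c descriptive mainly adds the paired n and removes any implied test. But the same section attaches ANOVA and p<0.05 to HOMA-IR, and a permissible reading is not a stated source when the only definition is under a discontinued heading.

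Two stronger readings are tempting and not supported. One is that the stop leaves too few men to compare. No paired count is given, and the 8 men of November 2016 are VO2peak completers, not men with paired insulin or CSA. The other is that a secondary objective and the metabolomics question can no longer be answered. The VO2peak half of that question is intact, the physiological objective keeps strength and endurance, and the metabolic objective keeps lean and fat mass.

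**Conclusion.** The inconsistency is real: Sections 5 and 12.5 promise comparisons on measures whose collection Section 9 ended, and the source and analysis set for HOMA-IR are unstated. As written, HOMA-IR is confined to men who reached Day 113 before the stop. Under the assumed 4 to 10 per arm, the detectable difference is roughly 1.5 to 2.6 times that at 20 per arm (1.32/0.91 and 2.38/0.91). The sponsor must supply the actual count.

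Deriving HOMA-IR from the stored plasma would remove that restriction but would not make the comparison well powered; the 11% figure assumes that the SD from the cited monotherapy study carries over. CSA cannot be recovered from plasma, and HgbA1c is not on the Table 2 panel. The primary endpoint is not touched.

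**What to change.** - **HOMA-IR (Sections 5, 9.12.3, 12.5):** state that it is derived for all men from the Table 2 fasting glucose and insulin in the baseline and Day 113 metabolomics plasma, using one platform for every man. Use the v1-v15 clinical values only to check agreement, not mixed into the analysis. Name the analysis set.
- **Reporting:** give between-arm estimates with 95% confidence intervals in place of the p<0.05 criterion. With an SD about four times the mean change (192.5/45.1 = 4.3), consider a log scale, which the transformation clause in 12.5 already allows.
- **Muscle CSA and HgbA1c:** mark them in Sections 5 and 12.5 as descriptive for the v1-v15 cohort, with paired n by arm and no between-arm test.

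**Cost:** wording in three sections, and no new visit or sample. It does depend on usable fasting aliquots at both time points and on both analytes being assayed as Table 2 plans; 9.12.3 sends the samples to storage for future analysis and gives no assay date. Insulin values may differ from the earlier clinical laboratory values, since its method on the panel is not specified. Glucose is less exposed, because 9.12.3 has conventional metabolites measured in a CLIA-certified clinical laboratory, as the earlier values were.
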